6. SCHEDULE OF EVENTS

Scheduled study visits, assessments, and dosing of each study drug will occur according to the Schedule of Events provided in Table 11. Every effort should be made to follow the schedule outlined in this table. Allowed visit windows are specified as follows:

- 1. Screening assessments must occur within 28 days or 21 days of Cycle 1 Day 1:
 - a. Vital signs, ECOG performance status, and physical exam should be performed within 28 days of start of study drug (Cycle 1 Day 1).
 - b. Specified laboratory and radiologic assessments should be performed within 21 days prior to the start of study drug (Cycle 1 Day 1).
- 2. Radiologic assessments must be performed as indicated in Table 11. A visit window of ±7 days is allowed. Even if study treatment doses are held for a patient, radiologic assessments should stay on schedule.
- 3. All other assessments have a general ± 3 -day window for completion with the exception of safety follow-up assessments that have a ± 5 -day window and the long-term follow-up assessments that have a ± 7 -day window.
- 4. A creatinine clearance determination should be performed monthly, and in case of a creatinine elevation while on-study.

Table 11: Schedule of Events

	Scree	ening ^a			ycle 1 3 days)		Cycl (21 da		Cycle 3+ (21 days)	EOT ^b	Safety F	ollow-up ^c	Long-Term	Follow-up ^d
											30 Days (±5 Days) After Last		Without PD (q12 weeks	With PD (q12 weeks
Day(s) of Cycle ^e	-28 to -1	-21 to -1	1	8	15	22	1	8	1		Dose	Dose	±7 days)	±7 days)
Study Day			1	8	15	22	29	36	50+					
Study Week			1	2	3	4	5	6	8+					
Obtain informed consent	X													
Enrollment/ Randomization			X											
Patient history	1				1	1								
Complete medical history	X													
Demography	X													
Prior antineoplastic therapies	X													
Inclusion/exclusion criteria	X													
Prior and concomitant medications	X		X	X	X	X	X	X	X	X	X ^f	X ^f		
Physical examination	X		X				X		X	X				
Weight	X		X				X		X	X				
Height	X													
ECOG performance status	X		X							X				
Vital signs ^g	X		X				X		X	X				
Laboratory assessments														
Hematology ^h		X	X	X	X	X	X	X	X	X				
Chemistryi		X	X	X	X	X	X	X	X	X				
Thyroid function tests ^j			X				Xqcycle2							
Creatinine clearance (Cockcroft-Gault estimation) ^k		X	X				X		X	X				
Coagulationh		X								X				
Urinalysis ¹		X												
Hepatitis serology ^m	X													
Serum pregnancy test ⁿ		X												

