7.4.1.2. Tumor Response Assessments

Tumor responses will be assessed by the Investigator per RECIST v1.1 (MRI or CT with contrast) and iRECIST (for patients receiving pembrolizumab). The CT scans should be performed with contrast unless contraindicated for medical reasons, in which case MRI should be used.

Although RECIST v1.1 will be the primary measure for assessment of tumor response and disease progression for efficacy endpoints, iRECIST guidelines should be used for treatment decision making for patients receiving pembrolizumab, including confirmation of unconfirmed progressive disease by RECIST v1.1 with additional imaging within 4 to 6 weeks (Appendix 3).

Investigator-determined response assessments at each assessment time point will be entered into the appropriate eCRF. Copies of all scans and redacted radiology reports are to be submitted according to vendor / Sponsor requirements in a timely manner.

All MRI or CT scan assessments will be determined from date of first dose and will follow the counting of calendar days and not the dosing cycles. It is critical that the same imaging modality used at screening is used throughout the study for each subject. The scans will be performed as follows:

- At Week 8 and then every 6 weeks (±7 days) for the first 26 weeks (6 months), and every 12 weeks thereafter for up to 1 year after permanent discontinuation of study treatment, until disease progression, the start of new anti-cancer treatment, withdrawal of consent, lost to follow-up, or the end of the study, whichever occurs first. A scan to confirm an unconfirmed PR or unconfirmed CR ≥4 weeks later may also be performed.
- At the EOT visit (unless the previous scan is within 4 weeks of the EOT visit).

If local regulatory authorities mandate less frequent imaging, the minimum frequency must be every 12 weeks.

All patients will be followed for disease progression or relapse using the schedule described in the Schedule of Events provided in Table 11. This includes patients who discontinue the protocol-specified treatments or the study early for any reason without documented evidence of progressive disease or relapse.

The radiologic assessments (MRI or CT with contrast) are considered the primary method of response assessment.

Patients who relapse or progress will continue to be followed for OS, all subsequent antineoplastic therapy, and response, including disease progression/relapse to subsequent antineoplastic therapy.

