9.6.1. Primary Efficacy Endpoint Analysis

For Phase 2, the primary efficacy endpoint is the determination of ORR, defined as the percentage of patients with a CR or PR within the first 26 weeks (6 months) of treatment as

assessed by the Investigator using RECIST v1.1. ORR will be summarized by dosing regimen with 95% CI obtained by Clopper-Pearson Exact methods and stratified by prior anti-PD-1 treatment exposure.

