CR: Disappearance of all non-target lesions and normalization of tumor marker levels. All lymph nodes must be non-pathological in size (< 10 mm in the short axis).

Non-CR/non-PD: Persistence of 1 or more non-target lesions or tumor marker levels maintained above normal limits.

PD: Unequivocal progression of existing non-target lesions or the appearance of 1 or more new lesions.

Overall Response

The following table shows the criteria for the assessment of overall response at each time point for subjects who have measurable lesions at baseline.

Evaluation of Overall Response at Each Time Point

Target Lesions	Non-Target Lesions	New Lesions	Overall Response
CR	CR	No	CR
CR	Non-CR/non-PD	No	PR
CR	Not evaluated	No	PR
PR	Non-PD/not evaluated	No	PR
SD	Non-PD/not evaluated	No	SD
NE	Non-PD	No	NE
PD	Any	Yes or no	PD
Any	PD	Yes or no	PD
Any	Any	Yes	PD

Source: RECIST version 1.1 criteria.

Abbreviations: CR = complete response; NE = not evaluable; PD = progressive disease; PR = partial response; RECIST = Response Evaluation Criteria in Solid Tumors; SD = stable disease.

Best Overall Response

Best overall response (BOR) in this study is defined as the BOR across all time points, eg, a subject who has SD at first assessment, partial response at second assessment, and PD at last assessment has a best overall assessment of PR. If SD is assessed as the BOR, it must also meet the SD criteria at least once after study entry at 6 weeks or longer from baseline. If SD is the best time point response and the minimum time requirement is not met, the subject's best response will depend on subsequent assessments eg, a subject who has SD at first assessment and PD at second assessment and does not meet the minimum duration for SD, will have a best overall assessment of PD. The same subject lost to follow-up after the first SD assessment would be considered unevaluable.

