All patients will be monitored at weekly intervals for the first 6 weeks, and then at 3-week intervals thereafter starting at Week 8. Tumor responses will be assessed at Week 8 and then every 6 weeks for the first 26 weeks (6 months) and every 12 weeks thereafter by the Investigator per Response Evaluation Criteria in Solid Tumors version 1.1 (RECIST v1.1). A scan to confirm an unconfirmed partial response (PR) or unconfirmed complete response (CR) ≥ 4 weeks later may also be performed.

Patients will continue to receive study drug until the development of progressive disease (per Investigator assessment), unacceptable toxicity, withdrawal of consent, Investigator's discretion, initiation of new antineoplastic therapy, or study termination by the Sponsor. The maximum treatment with pembrolizumab is 24 months.

The study design is summarized in [Figure 1](#) on the next page.

Figure 1 Study Design

CT = computed tomography; DLT = dose-limiting toxicity; EBV = Epstein-Barr virus; MRI = magnetic resonance imaging; NPC = nasopharyngeal carcinoma; RECIST v 1.1 = Response Evaluation Criteria in Solid Tumors Version 1.1; RM = recurrent and/or metastatic; RP2D = recommended Phase 2 dose; SDD = split daily dose

[1] Patients must have a histologically confirmed diagnosis of EBV⁺ recurrent or metastatic NPC or other solid tumor type and received previous systemic therapy for their cancer; have measurable disease determined by magnetic resonance imaging (MRI) or computed tomography with contrast at screening; and have adequate bone marrow, liver, and renal function.

[2] Starting nanatinostat dose is 20 mg once daily on Days 1 to 4 per week with valganciclovir 900 mg daily. Dose escalation of nanatinostat will continue with i) a total daily dose of 30 and 40 mg daily administered as a single dose on Days 1 to 4 per week with valganciclovir 900 mg once daily, ii) as a divided nanatinostat dose twice daily on Days 1 to 4 per week with valganciclovir 900 mg once daily or twice daily for 21 days followed by a subsequent dose reduction to 900 mg once daily, then iii) as a SDD of nanatinostat starting at 20 mg and valganciclovir at 450 mg twice daily 4 hours apart on Days 1 to 7 per week until the RP2D is determined.

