3.4 Efficacy and Safety Variables

3.4.1 *Efficacy Variables*

3.4.1.1 *Primary Efficacy Variable*

Tumor responses will be assessed by the Investigator per RECIST v1.1 using MRI or CT scan assessments. For patients receiving pembrolizumab, tumor responses will also be assessed per immunologic RECIST (iRECIST). Tumor imaging will be repeated to confirm disease progression using iRECIST.

The primary efficacy endpoint is ORR, defined as the percentage of patients with a CR or PR as assessed by RECIST v1.1 within the first 26 weeks (6 months) of treatment. The ORR will also be calculated using iRECIST for patients receiving pembrolizumab.

3.4.1.2 *Secondary Efficacy Variables*

Secondary efficacy endpoints include the following:

- Time to response (TTR) – defined as the interval from the start of study drug treatment to the date of first documented CR or PR per RECIST or iRECIST.
- Duration of response (DOR) – defined as the interval of time from the date of first observed CR or PR to the date of documented disease progression or death due to any cause, whichever occurs first. Dates of progression and censoring will be determined as described in [Section 4.5.5.2](#);
- Disease control rate (DCR) – defined as the percentage of patients having a CR, PR, or stable disease (SD) at any time during treatment;
- Progression-free survival (PFS) – defined as the interval of time from the start of study drug treatment to the date of first documented disease progression, initiation of new antineoplastic therapy, withdrawal of consent, loss to follow-up, or death due to any cause, whichever occurs first. Dates of progression and censoring will be determined as described in [Section 4.5.5.2](#); and
- Overall survival (OS) – defined as the interval of time from the start of study drug treatment to the date of death due to any cause. Patients without

documentation of death at the time of analysis will be censored at the date the patient was last known to be alive.

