4.5.3 Primary Efficacy Endpoint Analysis Methods

Counts and percentages for each tumor response category assessed by the Investigator per RECIST v1.1 will be presented by dosing regimen. Separate summaries will also be produced by prior anti-PD-1 treatment exposure. Non-evaluable patients are considered non-responders and will be included in the denominator. ORR estimates, from the first post-baseline assessment, with corresponding binomial 95% confidence intervals using the Clopper-Pearson Exact method will also be presented.

For patients receiving pembrolizumab, the analysis will be repeated using iRECIST.

Results from tumor assessments will be provided in separate listings.

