4.5.4 Secondary Efficacy Endpoint Analysis Methods

Disease control rate will be analyzed using the same statistical methodologies as applied to the primary efficacy endpoint in [Section 4.5.3](#).

Duration of response, PFS, and OS will be summarized in days using Kaplan-Meier methodology. The number of patients who experienced the event of interest and the number of patients censored will be presented, as will Kaplan-Meier product limit estimates of the 25th, 50th (median), and 75th percentiles with associated CIs (where estimable) using Greenwood's formula. The range for all patients, as well as those who experience the event of interest will also be summarized. Kaplan-Meier estimates of the survival distribution function over time will be generated for all patients receiving study treatment. The PFS and OS at 12 months (56 weeks) with associated 95% CIs will also be presented.

All derived efficacy measures will also be provided in a separate listing.

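### SAP 4.5.3, read literally, computes ORR from the first scan alone, which contradicts the 26-week ORR definition in SAP 3.4.1.1 and Protocol 9.6.1

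*SAP*

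**What the plan says.** SAP 3.4.1.1 defines the primary efficacy endpoint, ORR, as the percentage of patients with a "CR or PR as assessed by RECIST v1.1 within the first 26 weeks (6 months) of treatment". Protocol 9.6.1 uses the same window: "percentage of patients with a CR or PR within the first 26 weeks (6 months) of treatment". The efficacy assessments in the protocol synopsis agree.

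SAP 4.5.3, the methods section for this endpoint, provides for "ORR estimates, from the first post-baseline assessment, with corresponding binomial 95% confidence intervals using the Clopper-Pearson Exact method". It neither mentions 26 weeks nor refers to 3.4.1.1.

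SAP 3.1 schedules tumor assessments at Week 8, then 6-weekly to Week 26, then 12-weekly. Protocol Section 6 says of scans: "A visit window of ±7 days is allowed".

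SAP 4.8 records that the study stopped after Phase 1b and that ORR becomes a primary efficacy endpoint for that phase. It lists what it calls the only changes from the protocol. There are two, and neither concerns the ORR time window.

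**The concern.** A programmer implements the methods section. If 4.5.3 is taken at its word, response status is read from each patient's first post-baseline scan and nothing after it. A patient with stable disease at Week 8 and a partial response at Week 14 is a responder under 3.4.1.1 and a non-responder under 4.5.3. The same patient would still enter duration of response, because SAP 3.4.1.2 starts that endpoint at the first observed CR or PR, whenever it occurs.

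The sentence still matters although Phase 2 did not run, because it governs the only ORR that will be reported. SAP 4.1.1 tabulates by dosing regimen, and SAP 3.1 plans cohorts of 3 to 6 patients, so one reclassified patient visibly moves the estimate and its interval.

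**Working it through.** **1. The plan's own ORR figure.** SAP 4.7 says that with an ORR near 25% and n = 30 the 95% interval excludes 10%. The Clopper-Pearson limits are

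- lower = 0.025 quantile of Beta(x, n − x + 1)
- upper = 0.975 quantile of Beta(x + 1, n − x)

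The lower limit is 11.1% at a nominal 7.5/30, 12.3% at 8/30 and 9.93% at 7/30. The statement therefore reproduces at nominal 25% and at 8/30, but not at 7/30. The present point does not depend on it; this only checks the interval method.

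**2. Scans that count.** From the schedule in SAP 3.1: 8, 8 + 6 = 14, 14 + 6 = 20, 20 + 6 = 26, then 26 + 12 = 38.

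| Rule | Scheduled scans used |
|---|---|
| SAP 4.5.3, literal | Week 8 only (1 of the 4 in the window) |
| SAP 3.4.1.1 and Protocol 9.6.1 | Weeks 8, 14, 20, 26 |
| First scan onward, no limit taken from 3.4.1.1 | Weeks 8, 14, 20, 26, 38 and later |

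**3. Direction.** If the first scan falls inside 26 weeks, every responder under the literal rule is also a responder under the definition, but not the reverse. The literal ORR is therefore equal or lower. Without an end point, the onward rule gives an equal or higher ORR.

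**4. Size per patient.** One reclassified responder moves ORR by 100/n points: 33.3 at n = 3, 16.7 at n = 6, 14.3 at n = 7. Denominators can lie outside 3 to 6, because SAP 3.1 lets eligible patients already in screening join a cohort and the Full Analysis Set requires a post-baseline scan.

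**5. Illustration (assumed data).** Take one first response at Week 14 and one at Week 38, all other patients being non-responders.

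| n | Literal | 26-week definition | Onward, no limit |
|---|---|---|---|
| 6 | 0/6: 0% (0 to 45.9) | 1/6: 16.7% (0.4 to 64.1) | 2/6: 33.3% (4.3 to 77.7) |
| 3 | 0/3: 0% (0 to 70.8) | 1/3: 33.3% (0.8 to 90.6) | 2/3: 66.7% (9.4 to 99.2) |

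**6. Range over the unknown.** Let s be the share of 26-week responders already in response at Week 8. Then literal ORR = s × 26-week ORR. With the 25% of SAP 4.7 used only for scale, s = 50%, 60%, 80% and 100% give 12.5%, 15%, 20% and 25%. The documents do not give s.

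**7. The Week 26 scan.** Protocol Table 11 puts Week 8 at Day 50, so Week 26 starts on Day 50 + 18 × 7 = 176 and its ±7-day window runs from Day 169 to Day 183. If Week 26 instead means 26 full weeks after first dose, it is nominally Day 183 and the window ends on Day 190. Since 26 weeks is 182 days, a scan done within its window can fall after the limit under either count.

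**The case against.** The strongest reply is that ORR is a defined term. SAP 3.4.1.1 sits in the same document, and 4.5.3 only supplies methods for it. Read as that scan onward, 4.5.3 gives the start and 3.4.1.1 gives the end, and nothing conflicts. Two further readings are open. The synopsis plans response rates at each time point with exact intervals, so the phrase may introduce such a display. SAP 4.5.5.2 bases ORR on patients with baseline and post-baseline response assessments, so it may be a clumsy evaluability condition. Context also tells against a deliberate first-scan rule: SAP 3.4.1.2 adds time to response, which would vary little if only the first scan could show a response.

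Much of this stands. A reader might infer that no reading of 4.5.3 can yield the defined endpoint; the documents do not support that, because 3.4.1.1 can supply the limit. The protocol is not uniform either: the synopsis endpoint list and Table 3 define ORR without a window, although Table 3 points to 9.6.1 for methods. None of this rescues the literal reading, which is the plain sense of a phrase attached to the estimates themselves.

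It is also fair that results are descriptive, that no formal comparison or stopping rule uses this estimate, and that listed tumor assessments would let a reader rebuild the 26-week rate. Listings do not, however, correct the tabulated estimate and interval.

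**Conclusion.** The point holds for the literal reading. As written, SAP 4.5.3 counts one of four scheduled scans and contradicts the 26-week definition, with no change declared in SAP 4.8. The other readings agree with the definition only by borrowing a limit that 4.5.3 does not cite. The bias under the literal reading is zero or downward, provided first scans occur within 26 weeks. Its size is unknown, because the documents give neither the number nor the timing of responses.

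Three stronger inferences are not supported:

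- **That the Phase 1b ORR will be materially understated.** If every responder is already in response at the first scan, nothing changes.
- **That DCR is also wrong.** SAP 4.5.4 says "Disease control rate will be analyzed using the same statistical methodologies as applied to the primary efficacy endpoint", but 3.4.1.2 gives DCR its own definition, at any time during treatment, and the cross-reference most naturally covers the interval and the non-evaluable rule.
- **That Protocol Appendix 3 worsens the conflict.** It says "Best overall response (BOR) in this study is defined as the BOR across all time points", but 4.5.3 does not invoke best overall response.

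The correction should be made because the rule as stated can give a wrong primary estimate. It does not threaten the study's conduct or any test.

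**What to change.** In SAP 4.5.3, delete the phrase that ties ORR to the first assessment. Say instead that ORR counts a CR or PR per RECIST v1.1 at any post-baseline assessment in the first 26 weeks of treatment, with an explicit reference to Section 3.4.1.1. Add that the scheduled Week 26 scan counts if done within its ±7-day window, which settles the day-numbering question. A first-scan or by-time-point rate may stay as a separately labelled display.

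Optionally, add a clause to 4.5.4 saying that DCR keeps its own definition and shares only the interval and non-evaluable rules.

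The cost is one sentence, one window statement and the matching derivation. No new data are needed.

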4.5.4 Secondary Efficacy Endpoint Analysis Methods

Disease control rate will be analyzed using the same statistical methodologies as applied to the primary efficacy endpoint in [Section 4.5.3](#).

Duration of response, PFS, and OS will be summarized in days using Kaplan-Meier methodology. The number of patients who experienced the event of interest and the number of patients censored will be presented, as will Kaplan-Meier product limit estimates of the 25th, 50th (median), and 75th percentiles with associated CIs (where estimable) using Greenwood's formula. The range for all patients, as well as those who experience the event of interest will also be summarized. Kaplan-Meier estimates of the survival distribution function over time will be generated for all patients receiving study treatment. The PFS and OS at 12 months (56 weeks) with associated 95% CIs will also be presented.

All derived efficacy measures will also be provided in a separate listing.

4.5.5 Statistical/Analytical Issues

4.5.5.1 Adjustments for Covariates

There are no planned applications of covariate adjustments; all statistical results are descriptive in nature.

4.5.5.2 Handling of Dropouts or Missing Data

Objective response rate and disease control rate are based on those patients with available data (baseline and post-baseline response assessment). Non-evaluable patients are considered non-responders and will be included in the denominator. The analysis of PFS and DOR will be right-censored according to the conventions described in [Table 2](#). These conventions are based on the FDA Guidance for Industry *Clinical Trial Endpoints for the Approval of Cancer Drugs and Biologics* ([2018](#)) and *Clinical*

Trial Endpoints for the Approval of Non-Small Cell Lung Cancer Drugs and Biologics (2015).

Table 2 Conventions for Censoring for DOR and PFS

Situation	Date of Progression or Censoring	Outcome
No baseline tumor assessments	Randomization (if applicable), or enrollment	Censored
New anti-cancer treatment started before documentation of PD or death	Date of last disease assessment without documentation of PD before start of new treatment	Censored
Death or progressive disease (PD) immediately after more than one consecutively missed disease assessment visit	Date of last disease assessment visit without documentation of PD that is before the first missed visit	Censored
Alive and without PD documentation	Date of last disease assessment	Censored
Treatment discontinuation for undocumented progression, toxicity, or other reason	Date of last disease assessment without documentation of PD	Censored
Death or PD between planned disease assessments	Date of death or first disease assessment showing PD, whichever occurs first	Not Censored
Death or PD after more than one missed visit	Date of last disease assessment without documentation of PD	Censored

